C. difficile testing	X			X ^e									X					X ^e : Should be performed if clinical response is not achieved with extended induction. In addition, may be performed if loss of clinical benefit, per investigator discretion, on OL SC maintenance dosing. Additional local stool testing (e.g., ova and parasites) is allowed at the investigator’s discretion. V1 C. difficile testing does not need to be completed before the patient can start study drug therapy.
Fecal calprotectin and exploratory fecal biomarkers	X ^d			X								X	X					
Endoscopic Procedure																		
Endoscopy with biopsies				X								X	X					Please refer to Section 9.1.1.3 for procedure clarification.
UC Activity Assessments																		
Patient diary device dispensed	X																	

Procedure	Extended Induction			Open-Label Maintenance Period								Post-treatment Follow-up			Notes
	V1	V2	V3	V4 ^a	V5	V6	V7	V8	V9	V10	V11	V997	801	802	
Visit															
Week	0	4	8	12	16	20	24	28	32	36	40 LV	ETV	UV	LV +4	LV +12/16 ^c
Day and/or Visit Interval Tolerance	1 ^b	29 +/-3	57 +/-3	85 +/-7	113 +/-7	141 +/-7	169 +/-7	197 +/-7	225 +/-7	253 +/-7	281 +/-7		N/A	+/-10	+/-10
Patient diary compliance review		X	X	X	X	X	X	X	X	X	X	X	X		
PGA	X ^d			X							X	X			
Review Modified Mayo Score	X ^d			X							X	X			In addition, may be performed if loss of clinical benefit, per investigator discretion, on OL SC maintenance dosing
Patient diary device collected											X	X			
Health Outcome Assessments															
IBDQ	X ^d			X							X	X			
EQ-5D 5L	X ^d			X							X	X			
PGRC				X							X	X			
SF-36	X ^d										X	X			
WPAI:UC	X ^d										X	X			

Footnotes for Table AMBG.2.2

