Abbreviations: ADA = anti-drug antibody; AE = adverse event; anti-HBc+ = positive for anti-hepatitis B core antibody; BP = blood pressure; C-SSRS = Columbia-Suicide Severity Rating Scale; ECG = electrocardiogram; EIM = extraintestinal manifestation; EQ-5D 5L = European Quality of Life 5-Dimension 5 Level; ETV = early termination visit; FSH = follicle-stimulating hormone; HBsAg- = negative for hepatitis B surface antigen; HBV = hepatitis B virus; hsCRP = high-sensitivity C-reactive protein; IBDQ = Inflammatory Bowel Disease Questionnaire; IP = investigational product; IV = intravenous; IWRS = interactive web-response system; LV = last visit; N/A = not applicable; PGA = Physician's Global Assessment; PGRC = Patient's Global Rating of Change; PK = pharmacokinetic; PR = pulse rate; QIDS-SR16 = Quick Inventory of Depressive Symptomatology—Self-Report (16 Items); SC = subcutaneous; SF-36 = Medical Outcomes Study 36-Item Short Form Health Survey; T = temperature; UV = unscheduled visit; V = visit; WPAI:UC = Work Productivity and Activity Impairment Questionnaire Ulcerative Colitis.

Notes: All activities should be completed prior to any study drug administration unless otherwise stated. Last visit or ETV is last visit prior to entering long term extension Study AMAP or post-treatment follow-up. Post-treatment follow-up visits should only occur if the patient is not proceeding to long term extension Study AMAP or if they discontinue treatment in Study AMBG early (i.e. patients who do not achieve delayed clinical response).

- ^a For patients who cannot continue beyond V4 because they did not achieve delayed clinical response, ETV activities that are performed as part of V4 do not need to be repeated. Only those ETV activities that are not part of V4 should be completed during the ETV.
- ^b V1 (Week 0) should occur no more than 14 days from the start of the Visit 5/Week 12 visit of Study AMAN.
- ^c Patients who discontinue study drug with last dose administered IV will return for an LV +16 week post-treatment follow-up visit without a 12 week follow-up. Patients who discontinue study drug with last dose administered SC will return for an LV + 12 week post-treatment follow-up visit without a 16 week follow-up.
- ^d Results from V5 (Week 12) of Study AMAN will be used for Week 0 of this study.
- ^e Activity to be performed on a subpopulation of patients. See Notes column in table.
- ^f These tests will be run from the “chemistry” sample

3. Introduction

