5.1. Overall Design

Study AMBG is a Phase 3, multicenter, randomized, double-blind, placebo-controlled, parallel-arm study evaluating the safety and efficacy of 200 mg mirikizumab Q4W SC in maintaining treatment response at Week 40 (that is, 52 weeks of continuous therapy). The study also will evaluate the safety and efficacy of: (a) extended induction with 300 mg mirikizumab IV for patients who did not have a clinical response at Week 12 of Study AMAN, and (b) rescue induction for patients who achieved clinical response in Study AMAN and subsequently lose clinical response during Study AMBG.

Patient Population

Patients with moderately to severely active UC who completed Study AMAN and who meet eligibility requirements will enroll in this study. The study will enroll patients who achieve clinical response or clinical remission with blinded mirikizumab or placebo dosing in Study AMAN, as well as patients who do not achieve clinical response with blinded mirikizumab or placebo during Study AMAN.

Treatment Assignments

Maintenance study treatment assignment will be dependent on whether patients responded to study drug dosing in AMAN and whether they experience a loss of response (LOR) during this study as follows:

- **Mirikizumab Responders from Study AMAN**

Patients who achieve clinical response with blinded mirikizumab in induction Study AMAN will be randomized to receive blinded 200 mg mirikizumab Q4W SC or blinded placebo SC Q4W (randomized withdrawal) in a 2:1 ratio. Randomization will be stratified to achieve between-group comparability, based on biologic-failed status (yes or no), induction remission status (yes or no), baseline corticosteroid use (yes or no), and region (North America/Europe/Other).

Patients will continue on the randomized treatment assignment for the remainder of Study AMBG unless they develop secondary LOR.

Loss of Response (LOR) is defined as:

- ≥ 2 -point increase from Study AMBG baseline in the combined SF + RB scores AND combined SF + RB score of ≥ 4 , on 2 consecutive visits (≥ 7 days apart), and with confirmation of negative *C. difficile* testing (first assessment can start as early as Week 8/Visit 3),

AND

- Confirmed by centrally read endoscopic subscore (ES) of 2 or 3 not sooner than Week 12/Visit 4.

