Patients who achieve delayed clinical response (compared to induction study baseline) with extended mirikizumab induction therapy at Week 12 may subsequently receive open-label 200 mg mirikizumab Q4W SC starting at Week 12. Patients will continue on this dose regimen and undergo endoscopy at Week 40. Patients who, in the opinion of the investigator, receive clinical benefit may be considered for enrollment into the long term extension study AMAP to receive further SC dosing. Patients who discontinue study drug before Week 40 will undergo endoscopy and procedures for early termination of the study drug, including post-treatment follow-up as described in the schedule of activities (Section 2).

Patients who do not achieve clinical response to mirikizumab IV extended induction therapy at Week 12, compared to induction baseline, will discontinue study drug and undergo procedures for early termination of the study drug, including post-treatment follow-up as described in the schedule of activities (Section 2).

Post-Treatment Follow-up Period

Patients will undergo a maximum 16-week post-treatment follow-up period:

- Patients who discontinue study drug with **last dose administered IV** will return for post-treatment follow-up visits (Visit 801 and 802) at 4 and 16 weeks after the end-of-treatment visit.
- Patients who discontinue study drug with **last dose administered SC** will return for post-treatment follow-up visits (Visit 801 and 802) at 4 and 12 weeks after the end-of-treatment visit.
- Patients who subsequently enter the long term extension study AMAP do not need to complete the post-treatment follow-up period.

Figure AMBG.5.1 illustrates the study design. Study governance considerations are described in detail in Appendix 3.

[figure not shown]

Figure AMBG.5.1. Illustration of study design for Clinical Protocol I6T-MC-AMBG.

Footnotes for Figure AMBG.5.1

Abbreviations: D/C = discontinue; IV = intravenous; LOR = loss of response; Miri = mirikizumab; OL = open-label; PBO = placebo; Q4W = every 4 weeks; R = randomization; RB = rectal bleeding; SC = subcutaneous; SF = stool frequency; W = week.

Note: LOR is defined as ≥ 2 -point increase from maintenance baseline in the combined SF + RB scores, AND combined SF + RB score of ≥ 4 on 2 consecutive visits, AND confirmed by an endoscopic subscore of 2 or 3.

a = Loss of response at or after Week 12 and up to and including Week 28.

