Abbreviations: IV = intravenous; LOR = loss of response (defined as ≥ 2 -point increase from maintenance baseline in the combined SF + RB scores, AND combined SF + RB score of ≥ 4 on 2 consecutive visits, AND confirmed by endoscopic subscore of 2 or 3); OL = open-label; Q4W = every 4 weeks; RB = rectal bleeding; SC = subcutaneous; SF = stool frequency.

Table AMBG.7.2. Treatment Regimens: Induction Clinical Nonresponders

Regimen	Dose Weeks 0-8	Dose Weeks 12-40
Nonresponders to blinded mirikizumab IV in induction study		
Open-label 300 mg mirikizumab IV	Weeks 0, 4, 8	Week 12 Extended Induction Responders 
 • Open-label 200 mg mirikizumab SC at Weeks 12, 16, 20, 24, 28, 32, 36; then may proceed to Study AMAP • If clinical benefit is lost, discontinue mirikizumab and enter post-treatment follow-up period Week 12 Extended Induction Nonresponders: 
 • Discontinue mirikizumab
Nonresponders to blinded placebo in induction study		
Open-label 300 mg mirikizumab IV	Weeks 0, 4, 8	Week 12 Extended Induction Responders 
 • Open-label 200 mg mirikizumab SC at Weeks 12, 16, 20, 24, 28, 32, 36; then may proceed to Study AMAP • If clinical benefit is lost, discontinue mirikizumab and enter post-treatment follow-up period Week 12 Extended Induction Nonresponders: 
 • Discontinue mirikizumab

Abbreviations: IV = intravenous; SC = subcutaneous.

Study Drug Administration

Subcutaneous administration of mirikizumab or placebo will be given in 2 injections (maximum volume is 1 mL per injection).

Intravenous infusion of mirikizumab will occur over at least 30 minutes. All patients should be monitored for 1 hour or longer after dosing, or longer according to investigator practice or local standard of care. Sites must have resuscitation equipment, emergency medications, and appropriately trained staff available during the infusion and monitoring period. Detailed instructions for investigational product administration will be provided separately by the sponsor.

Investigational product will be prepared at the site by blinded pharmacists or other trained and qualified personnel as designated by the investigator. Investigational product will be administered at the site by a blinded nurse, pharmacist, or other trained and qualified personnel as designated by the investigator.

The investigator or his/her designee is responsible for the following:

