- Induction study responders who experience LOR and do not receive clinical benefit from mirikizumab IV rescue induction
- Induction study nonresponders who do not achieve clinical response with 3 doses of mirikizumab IV extended induction
- Induction study nonresponders who achieve clinical response with mirikizumab extended IV induction, but subsequently lose clinical benefit with open-label mirikizumab SC dosing, should be discontinued. Loss of clinical benefit may be based on demonstrating LOR criteria (see Section 5.1) or by other criteria according to investigator discretion
- Patients who require treatment with a prohibited UC medication ([Appendix 8](#)), an increase in immunomodulatory medication, or a course of corticosteroids that exceeds the baseline dose
- Patients who undergo surgery for UC

Safety Criteria for Study Drug Discontinuation

- The patient requires a prohibited medication to treat their UC ([Appendix 8](#)). A patient who initiates a prohibited medication for a non-UC indication may either discontinue the study drug, or discontinue the prohibited medication.
- The patient requires a colectomy, proctocolectomy, or partial colectomy during the study.
- A diagnosis of cancer, other than squamous cell or basal cell carcinoma of the skin, during the study.
- Dysplasia occurring in flat mucosa or DALM.
- A diagnosis of active TB during the study.
- A diagnosis of HIV/AIDS during the study.
- A diagnosis of hepatitis B during the study or development of detectable HBV DNA during the study (see Section [9.4.5.2](#)).
- A diagnosis of hepatitis C during the study or development of detectable hepatitis C virus (HCV) RNA during the study (see Section [9.4.5.4](#)).
- The patient becomes pregnant. Pregnant patients **will not** undergo an endoscopy at the ETV.
- The participant has an AE or SAE which, in the opinion of the investigator or sponsor, would preclude the participant from continuing to receive study drug.

- Systemic hypersensitivity event or anaphylaxis to study drug.

It is recommended that the patient be assessed by an appropriately trained professional to assist in deciding whether the patient is to be discontinued from the study if:

- The patient scores a 3 for Item 12 (Thoughts of Death or Suicide) on the Quick Inventory of Depressive Symptomatology—Self-Report (16 Items) (QIDS-SR16) at any time in the study, or
- The patient reports suicidal ideation or suicide-related behaviors during the study

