9.1.1.3. Endoscopy

Endoscopy will be used to determine the Mayo ES at the time points described in the Schedule of Activities (Section 2).

Flexible sigmoidoscopy is the standard endoscopic procedure for assessment of endoscopic disease activity in this study. However, colonoscopy can be performed instead of flexible sigmoidoscopy within this study in order to surveil for dysplasia, screen for colorectal cancer (see Inclusion Criterion [5]), or for other clinically indicated reasons, in the judgement of the investigator and after discussion with the medical monitor as appropriate.

Endoscopic disease activity assessed at Week 12 of Study AMAN will serve as the baseline assessment of endoscopic disease activity in Study AMBG.

In patients who enter Study AMBG in clinical response or clinical remission, endoscopy will be performed at Week 40, ETV, UV, or if LOR is suspected in these patients based on SF/RB scores, endoscopy can be performed at or after Week 12 to confirm secondary LOR. Secondary LOR must be confirmed endoscopically before rescue mirikizumab IV induction dosing is initiated. If endoscopy does not confirm secondary LOR, patients are encouraged to continue study drug dosing. If study drug dosing is continued, an additional endoscopy would be performed at Week 40, ETV, or UV.

In patients who enter Study AMBG as induction study nonresponders, endoscopy will be performed at Week 12, following extended mirikizumab IV induction. An additional endoscopy will be performed at Week 40, ETV, or UV. Patients who plan to continue in the long term extension study AMAP and who require an annual surveillance colonoscopy to remain up-to-date in screening for colorectal cancer (see Inclusion Criterion [5]), will undergo colonoscopy as the endoscopy method at Week 40.

If a patient becomes pregnant during the study, no additional endoscopies will be performed.

If a patient undergoes early termination soon after baseline, loss of response, or at the end of extended induction endoscopy, the need for ETV endoscopy should be discussed with the medical monitor.

The endoscopy report and histopathology report (if biopsies are sent to a local histopathology laboratory) must be available in the source documents.

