Severe disease	3
Mayo Score = Stool Frequency (SF) + Rectal Bleeding (RB) + Endoscopic Subscore (ES) + Physician's Global Assessment (PGA)	

Note: The Mayo score ranges from 0 to 12, with higher scores indicating more severe disease. Modified Mayo score excludes PGA and ranges from 0 to 9. Composite SF and RB score ranges from 0 to 6. The original description of the Mayo score included friability in the definition of an ES of 1. Consistent with current clinical practice and regulatory guidance, this study excludes friability from the definition of an ES of 1.

Stool frequency reports the number of stools in a 24-hour period, relative to the normal number of stools for that patient. The reference "normal" stool frequency for that patient will be recorded electronically at the screening visit in Study AMAN. The Normal SF refers to when the patient was in remission or, if the patient has never achieved remission, the reported SF before initial onset of signs and symptoms of ulcerative colitis. Remission refers to a period of time since being diagnosed with ulcerative colitis when the patient is not experiencing any signs or symptoms relating to ulcerative colitis. This period of time may last a few weeks or a few months or may even last several years. The patient will record this electronically as source data in the tablet device at the screening study visit in Study AMAN.

Source: Adapted from Schroeder et al. (1987) and Scherl et al. (2009)

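### Section 8.1.1 offers the Section 5.1 LOR criteria for extended-induction responders, but these measure the SF+RB rise from a visit at which the patients were nonresponders, so a return to that score never meets LOR

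*Protocol*

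**What the plan says.** Section 8.1.1 covers AMAN nonresponders who reach clinical response on extended IV induction and later lose benefit on open-label SC mirikizumab. They should be discontinued, and the protocol gives two ways to judge the loss: "Loss of clinical benefit may be based on demonstrating LOR criteria (see Section 5.1) or by other criteria according to investigator discretion".

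Section 5.1 defines LOR under its heading for patients who responded to mirikizumab in AMAN. The symptom part is a 2-or-more "point increase from Study AMBG baseline in the combined SF + RB scores", together with a combined score of at least 4, on two consecutive visits at least 7 days apart and with negative *C. difficile* testing. The endoscopic part is a centrally read ES of 2 or 3, not before Week 12.

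For induction nonresponders, footnote d of Table AMBG.2.2, which is attached to the Week 0 modified Mayo score, states: "Results from V5 (Week 12) of Study AMAN will be used for Week 0 of this study". Section 9.1.1.3 agrees for endoscopy: "Endoscopic disease activity assessed at Week 12 of Study AMAN will serve as the baseline assessment of endoscopic disease activity in Study AMBG". The notes to Figure AMBG.5.1 and Table AMBG.7.1 word the LOR reference differently, as an "increase from maintenance baseline in the combined SF + RB scores".

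The operative instruction in Table AMBG.7.2 does not mention LOR: "If clinical benefit is lost, discontinue mirikizumab and enter post-treatment follow-up period".

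**The concern.** The LOR definition was built for patients who enter AMBG in response. Their AMBG baseline is their improved state, so a rise from it signals a relapse. Section 8.1.1 carries the same definition over to patients whose AMBG baseline is their unimproved state and whose improvement comes 12 weeks later, and it does not move the reference point.

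The criterion then asks whether the patient is worse than when extended induction began. The question that matters is whether the response gained at Week 12 has been lost. A patient who gives up all of that gain and no more scores as having no loss of response. At stake are the usefulness of the one scored criterion that Section 8.1.1 names and the consistency with which sites stop similar patients in the open-label cohorts.

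**Working it through.** The protocol gives no figure to reproduce here. The check is to apply the rule as written.

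**Inputs**
- Rise of at least 2 and score of at least 4: Section 5.1.
- Reference visit: Study AMBG baseline (Section 5.1), which for this cohort is AMAN Week 12 (Table AMBG.2.2 footnote d; Section 9.1.1.3).
- Scale: "Composite SF and RB score ranges from 0 to 6" (Appendix 6).
- Response definition: Table AMBG.9.1, judged against induction baseline (Section 5.1).

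**Step 1. Score needed.** With S0 the Week 0 SF+RB score, the symptom part needs S ≥ max(S0 + 2, 4).

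| S0 | Score needed | Reachable on 0–6? | Met by a return to S0? |
|---|---|---|---|
| 0 | max(2, 4) = 4 | yes | no |
| 1 | max(3, 4) = 4 | yes | no |
| 2 | max(4, 4) = 4 | yes | no |
| 3 | max(5, 4) = 5 | yes | no |
| 4 | max(6, 4) = 6 | only at the maximum | no |
| 5 | max(7, 4) = 7 | no | no |
| 6 | max(8, 4) = 8 | no | no |

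A return to S0 is a rise of S0 − S0 = 0, below 2 for every S0. This follows from the rule itself and depends on no data. It also holds if SF and RB are carried as unrounded three-day averages (Section 10.3.3.1); in that case any S0 above 4 puts LOR out of reach.

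**Step 2. A relapse that LOR misses.** SF+RB is 5 at Week 0, 1 at AMBG Week 12 and 5 again at Week 24. As written, the rise is 5 − 5 = 0: not LOR. Measured from Week 12, the rise is 5 − 1 = 4 to a score of 5: the symptom part is met.

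**Step 3. A relapse that LOR catches.** Take SF/RB/ES as follows.
- Induction baseline 3/2/3: MMS 8.
- Week 0 2/1/3: MMS 6, a fall of 2 and 2/8 = 25%, below the required 30%, so a nonresponder.
- AMBG Week 12 1/0/1: MMS 2, a fall of 6 and 6/8 = 75%, with RB 0, so a responder.
- Relapse to 3/2/3: SF+RB moves from 3 at Week 0 to 5, a rise of 2 to a score of at least 4, with ES 3.

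The LOR score criteria are met as written, because this patient had partly improved by Week 0 and then became 2 points worse than at AMBG entry.

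**Step 4. What re-anchoring leaves open.** Induction baseline 3/2/3 (MMS 8); Week 0 3/1/3 (MMS 7, a fall of 1, nonresponder); AMBG Week 12 2/1/1 (MMS 4, a fall of 4 and 50%, RB 1, responder); then back to 3/1/3. From Week 12 the SF+RB rise is 4 − 3 = 1, so LOR is still not met. A Week 12 reference does not catch every relapse.

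**The case against.** The strongest reply is that nothing depends on this criterion. Section 8.1.1 makes LOR optional beside discretion, its list of reasons is expressly not exhaustive, and Table AMBG.7.2 stops treatment on loss of benefit with no LOR test. This stands, and it sets the size of the point. A reader might infer that relapsed patients must be kept on drug. The documents do not support that: failing LOR obliges no one to continue dosing.

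A reader might also infer that LOR misses every full relapse in this cohort. It does not. A return to a worse induction baseline can meet it, as Step 3 shows. What it always misses is a return to the AMBG Week 0 score.

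Nor is LOR the only scored means available. It is the only one that Section 8.1.1 names, but Table AMBG.2.2 says of the modified Mayo score review: "In addition, may be performed if loss of clinical benefit, per investigator discretion, on OL SC maintenance dosing". An investigator may therefore apply a scored judgement under the discretionary route.

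Finally, one could argue that the maintenance-baseline wording in the figure and table notes lets a site use Week 12, since Table AMBG.2.2 labels Week 12 onward as the open-label maintenance period for these patients. This is weak. Exclusion criterion 8 places maintenance baseline at AMAN Visit 5 (Week 12), and Section 8.1.1 cites Section 5.1, which names Study AMBG baseline. The general rule in Section 10.3.1 that efficacy baseline means induction baseline yields to that explicit wording.

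**Conclusion.** The point holds and is minor. The LOR criteria that Section 8.1.1 cites have the wrong reference visit for extended-induction responders: a return to the Week 0 score never qualifies, Week 0 scores of 5 or 6 can never qualify, and lower scores qualify only when the patient is at least 2 points worse than at AMBG entry. This rests only on the stated definition, the stated baseline and the 0 to 6 scale.

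Only the scored criterion named in Section 8.1.1 is affected and, through it, the consistency of stopping in the open-label cohorts, which Section 10.3.1 analyses descriptively without testing. A reader might infer some effect on the trial's main result. There is none: the randomized cohort uses the LOR definition as designed, and the primary endpoint and the Week 12 extended-induction endpoints do not depend on this rule.

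The number of patients affected cannot be estimated, because the protocol gives no delayed-response rate, relapse rate or Week 0 score distribution. Counts of possible score combinations would not substitute for these, since combinations are not patients.

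**What to change.** State in Section 8.1.1 that, for extended-induction responders, the rise of at least 2 points is measured from the AMBG Week 12 (Visit 4) SF+RB score. Keep the combined score of at least 4, ES 2 or 3, negative *C. difficile* testing and the discretionary route. Discretion must stay, because a relapse within 1 point of the Week 12 score would still not meet LOR (Step 4). If the sponsor prefers no scored criterion for this cohort, deleting the cross-reference to Section 5.1 also removes the fault.

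The cost is one sentence and a short clarification to sites. No visit or procedure is added, since Table AMBG.2.2 already schedules review of the modified Mayo score at Visit 4.
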